1.2.1 Estimands

Primary estimand defined for main endpoints are summarized in [Table 1](#). More details are provided in [Section 3.2](#) and [Section 3.3](#).

Table 1 - Summary of primary estimand for the main endpoints

| Endpoint Category | Estimand | | | |
|------------------------------------------------------------------------------------------------------------------------------------------------------------|------------------------------------------------------------------------------------|------------|-----------------------------------------------------------------------------------------------------------------------------------------------------------------------------------------------------------------------------------------------------------------------------------------------------------------------|---------------------------------------------------------------------------------------------------------------------------------------------|
| | Endpoint | Population | Intercurrent event(s) handling strategy and missing data handling | Population-level summary |
| Primary objective: To evaluate the efficacy of dupilumab in children from Japan who are 6 to <12 years of age with uncontrolled, persistent asthma. | | | | |
| Primary endpoint - continuous | Change from baseline in pre-bronchodilator % predicted FEV1 at Week 12 | ITT | 
The intercurrent events (IEs) will be handled as follows:
 
 • Discontinuing the study intervention before Week 12: all data collected after discontinuation will be used in the analysis (treatment policy strategy). 
Missing data will not be imputed.
 | 
Descriptive statistics and 95% confidence interval (CI) of the mean change from baseline (based on t-distribution) will be provided.
 |
| Secondary endpoint – count data | Annualized rate of severe asthma exacerbation events, during the treatment period. | ITT | 
The following IE will be handled with treatment policy strategy. All assessments after starting such IE will be included.
 
 • Discontinuing the study intervention 
Missing data will not be imputed.
 | 
The unadjusted annualized severe exacerbation event rate will be presented.
 |

Additional secondary objectives/endpoints are not included in this table but would be handled with a similar strategy as the endpoint type.

2 ANALYSIS POPULATIONS

The following populations for analyses are defined. The primary population of the efficacy endpoints is the ITT population.

Table 2 - Populations for analyses

| Population | Description |
|--------------------------|--------------------------------------------------------------------------------------------------------------------------------------------------------------------------------------------------------------------------------------------------------------------------------------------|
| Screened | All participants who signed the informed consent/assent. |
| Enrolled | All participants who signed the informed consent/assent and had a treatment kit number allocated and recorded in the IVRS/IWRS database, regardless of whether the treatment kit was received or not. |
| Intent-to-treat (ITT) | All participants in the enrolled population. Participants will be analyzed according to the dose regimen as enrolled. |
| Safety | All enrolled participants who have taken at least 1 dose of study intervention, regardless of the amount of treatment administered. Participants will be analyzed according to the dose regimen they actually received. |
| Pharmacokinetic (PK) | The PK population includes all participants in the safety population who had at least 1 non-missing and evaluable predose serum concentration value after the first dose of dupilumab in the study. Participants will be analyzed according to the dose regimen they actually received. |
| Anti-drug antibody (ADA) | ADA population includes all participants in the safety population with at least 1 non-missing ADA result following the first dose of dupilumab in the study. Participants will be analyzed according to the dose regimen they actually received. |

3 STATISTICAL ANALYSES

3.1 GENERAL CONSIDERATIONS

In general, continuous data will be summarized using the number, mean, standard deviation (SD), median, minimum, and maximum for observed data and the change from baseline. Categorical and ordinal data will be summarized using the count and percentage of participants.

The baseline values for efficacy, safety, PK, ADA and other endpoints are defined as the last available measurements prior to the first IMP dose if the participant is treated, or the last available value up to enrollment if the participant is not exposed to IMP.

Unless otherwise specified, all analyses will be performed on each dose regimen group and overall.

Observation period

The observation period will be divided into 4 segments:

- The **pre-treatment period** is defined as the period up to first IMP administration.
- The **treatment-emergent (TE) period** is defined as the period from the first IMP administration to the last IMP administration + 98 days for participants with IMP on 100 mg/200 mg q2w regimen, or to the last IMP administration + 112 days for participants on 300 mg q4w regimen. The treatment-emergent period includes the following 2 periods:
 - The **on-treatment period** is defined as the period from the first IMP administration to the last administration of the IMP + 14 days for participants with IMP on 100 mg/200 mg q2w regimen, or to the last administration of IMP + 28 days for participants on 300 mg q4w regimen.
 - The **residual treatment period** is defined as the period from the end of the on-treatment period to the end of the treatment-emergent period.
- The **post-treatment period** is defined as the period from the end of the treatment-emergent period.

The on-study observation period is defined as the time from start of intervention until the end of the study defined as the status date collected on e-CRF page “Completion of End of Study”.

3.2 PRIMARY ENDPOINT ANALYSIS

The primary endpoint is the change from baseline in pre-bronchodilator percentage (%) predicted FEV1 at Week 12. The primary endpoint will be analyzed on the ITT population. Intercurrent events (IE) handling strategies are described below:

- The IE of discontinuing the study intervention before Week 12 will be handled with the treatment policy strategy. Data collected after such IEs will be included.

No missing data will be imputed. Descriptive statistics (number of participants, mean, SD, median, minimum and maximum) and 95% CI of the mean (based on t-distribution) will be provided.

3.3 SECONDARY ENDPOINTS ANALYSIS

Efficacy secondary endpoints are described in this section. Non-efficacy secondary endpoints analyses are defined in [Section 3.5.2](#) (AE, SAE), [Section 3.5.3.1](#) (laboratory abnormalities and vital signs), [Section 3.6.1.1](#) (PK), [Section 3.6.1.2](#) (immunogenicity), and [Section 3.6.1.3](#) (biomarkers).

Statistical analyses for efficacy secondary endpoints will be conducted on the ITT population.

Annualized rate of severe asthma exacerbation events

A severe exacerbation event during the study is defined as a deterioration of asthma requiring:

- Use of SCS for ≥ 3 days; or,
- Hospitalization or emergency room visit because of asthma, requiring SCS.

The annualized rate of severe exacerbation events is defined as the total number of severe exacerbation events with onset period from enrolled up to the Week 52 visit or last contact date (whichever comes earlier) per participant-year. The IE of discontinuing the study intervention will be handled with the treatment policy strategy. Data after such IEs will be included. For discontinuation of the study follow-up before Week 52, all observed events up to the time of study discontinuation will be included, and the observation duration is defined as from enrollment to the time of study discontinuation. No imputation will be performed for the unobserved events that may happen after the study discontinuation.

The number of participants with one or more severe exacerbation events (number and qualitative variable: Yes/No), number of severe exacerbation events (qualitative variable: 0, 1, 2, 3, ≥ 4), total number of severe exacerbation events, total participant-years, unadjusted annualized severe exacerbation event rate, and duration (days) of a single severe exacerbation (number, mean, SD, median, minimum, maximum) during the treatment period will be presented. Unadjusted annualized rate will also be analyzed for severe exacerbation with use of SCS for ≥ 3 days only, and those with hospitalization or with emergency room visit only.

Change from baseline in lung function measurements

For change from baseline in pre-bronchodilator % predicted FEV1, absolute FEV1, FVC, and FEF 25%-75%, IE handling strategies are similar to the primary endpoint. Descriptive statistics (number of participants, mean, SD, median, minimum and maximum) and the 95% CI (based on t-distribution) of the mean will be presented over visits (Weeks 2, 4, 8, 24, 52, 64 for % predicted FEV1, and Weeks 2, 4, 8, 12, 24, 52, 64 for the others). In addition, figure of mean change from baseline (with corresponding standard error) will be presented for the parameter over visits.

Change from baseline in ACQ-IA

The global ACQ-7-IA score is the mean of the 7 questions of the Asthma Control Questionnaire—Interviewer Administered, 7-question version (ACQ-IA-7), and global ACQ-5-IA is the mean of the first 5 items.

For change from baseline in global ACQ-5-IA and ACQ-7-IA scores, IE handling strategies are similar to the primary endpoint. The methods for handling missing values of the questions are described in [Section 5.4](#). No missing data imputation will be performed for the global scores. Descriptive statistics (number of participants, mean, SD, median, minimum and maximum) and the 95% CI (based on t-distribution) of the mean will be presented over visits. Figure of mean change from baseline (with corresponding standard error) will be presented over visits.

3.4 MULTIPLICITY ISSUES

Not applicable.

3.5 SAFETY ANALYSES

All safety analyses will be performed on the safety population, unless otherwise specified, using the following common rule:

- The analysis of the safety variables will be essentially descriptive, and no testing is planned.

3.5.1 Extent of exposure

The extent of IMP exposure will be assessed by the duration of IMP exposure and compliance and summarized within the safety population by dose regimen group and overall.

Duration of IMP exposure

Duration of IMP exposure is defined as last IMP administration date – first IMP administration date + 15 days for the q2w regimens or + 29 days for the q4w regimen, regardless of unplanned intermittent discontinuations. If the date of the last dose of IMP is missing, the duration of IMP will be left as missing.

Duration of IMP exposure will be summarized descriptively as a quantitative variable (number, mean, SD, median, minimum, and maximum). In addition, duration of treatment exposure will also be summarized categorically by numbers and percentages for each of the following categories and cumulatively according to these categories: >0 and ≤2 weeks, >2 and ≤4 weeks, >4 and ≤8 weeks, >8 and ≤12 weeks, >12 and ≤16 weeks, ...>48 and ≤52 weeks, >52 weeks.

Additionally, the cumulative duration of treatment exposure will be provided in participant-years overall.

Treatment compliance

A given administration will be considered noncompliant if the participant did not receive the number of administration as required by the protocol.

Percentage of treatment compliance for a participant will be defined as the number of administrations that the participant was compliant divided by the total number of administrations that the participant was planned to take from the first administration of IMP up to the actual last administration of IMP.

Treatment compliance percentages will be summarized descriptively as quantitative variables (number, mean, SD, median, minimum, and maximum). The percentage of participants whose compliance is <80% will be summarized.

Cases of overdose of IMP (defined as at least twice the intended dose during an interval of less than 11 days for 100/200 mg q2w regimen or less than 25 days for 300 mg q4w regimen) will be summarized by numbers and percentages of participants with at least 1 overdose.

3.5.2 Adverse events

General common rules for adverse events

All adverse events (AEs) will be coded to a lower-level term (LLT), preferred term (PT), high-level term (HLT), high-level group term (HLGT), and associated primary system organ class (SOC) using the Medical Dictionary for Regulatory Activities (MedDRA) version currently in effect at Sanofi at the time of database lock.

The AEs will be analyzed in the following 3 categories:

- Pre-treatment AEs: AEs that developed, worsened or became serious during the pre-treatment period
- Treatment-emergent adverse events (TEAEs): AEs that developed, worsened or became serious during the treatment-emergent period
- Post-treatment AEs: AEs that developed, worsened or became serious during the post-treatment period

The primary AE analyses will be on TEAEs. Pre-treatment and post-treatment AEs will be described separately if applicable.

An AE with incomplete or missing date/time of onset (occurrence, worsening, or becoming serious) will be classified as a TEAE unless there is definitive information to determine it is a pre-treatment or a post-treatment AE.

If the assessment of the relationship to IMP is missing for an AE, this AE will be assumed as related to IMP. Missing severity will be left as missing.

The AE incidence tables will summarize the number (n) and percentage (%) of participants experiencing at least one AE in safety population. Multiple occurrences of the same event in the same participant will be counted only once in the tables. The denominator for computation of percentages is number of participants in safety population.

The AE tables will be sorted as indicated in [Table 3](#).

Table 3 - Sorting of AE tables

| AE presentation | Sorting rules |
|------------------------|----------------------------------------------------------------------------------------|
| SOC, HLGT, HLT and PT | By the internationally agreed SOC order and by alphabetic order of HLGTs, HLTs and PTs |
| SOC and PT | By the internationally agreed SOC order and decreasing frequency of PTs |
| SMQ/CMQ and PT | By decreasing frequency of SMQs/CMQs and PTs |

Analysis of all adverse events

The overview of TEAE with the details below will be generated:

- Any TEAE
- Any severe TEAE
- Any treatment-emergent SAE
- Any TEAE leading to death
- Any TEAE leading to permanent study intervention discontinuation
- Any treatment-emergent AESI
- Any treatment-emergent other selected AE grouping
- Any treatment-emergent AE related to IMP

The AE summaries of [Table 4](#) will be generated to summarize the number (%) of participants experiencing at least one event.

Table 4 - Analyses of adverse events

| Type of AE | MedDRA levels |
|----------------------------------------------|-------------------------------|
| All TEAE | Primary SOC, HLGT, HLT and PT |
| All TEAE | Primary SOC and PT |
| TEAE related to IMP | Primary SOC and PT |
| Treatment-emergent SAE | Primary SOC and PT |
| TEAE leading to intervention discontinuation | Primary SOC and PT |
| TEAE leading to death ^a | Primary SOC and PT |
| TEAE related to COVID-19 | Primary SOC and PT |

^a Death as an outcome of the AE as reported by the Investigator in the AE page

Analysis of adverse events of special interest (AESIs) and other selected AE groupings

Adverse events of special interest (AESIs) and other selected AE grouping defined in [Table 5](#) will be selected for analyses. Tables will be sorted as indicated in [Table 3](#).

Table 5 - Criteria for AESIs and other selected AE groupings

| AE Grouping | Criteria |
|---------------------------------------------------------------------------------------------------|---------------------------------------------------------------------------------------------------------------------------------------------------------------------------------------------------------------------------------------------------------------------------------------------------------------------------------------------------------------------------------------------------------------------------------------------------------------------------------------------------------------------------------------------------------------------------------------------------------|
| AESI | |
| Anaphylactic reaction | Anaphylactic reaction algorithmic approach (Introductory Guide for Standardised MedDRA Queries (SMQs) Version 18.1): includes anaphylactic reaction narrow SMQ (20000021) terms and programmatic identification of cases based on occurrence of at least two preferred terms meeting the algorithm criteria occurring within 24 hours of each other. The latter cases identified using the algorithm will undergo blinded medical review taking into account the timing of events relative to each other and to IMP administration for final determination of an anaphylactic reaction or not. |
| Hypersensitivity (medically reviewed) | Hypersensitivity narrow SMQ (20000214) and [AE corrective treatment/therapy='Yes' or Action taken with IMP='Drug withdrawn' or Action taken with IMP='Drug interrupted'] followed by medical review (documented process) for selection of relevant systemic hypersensitivity events |
| Severe injection site reactions that last longer than 24 hours or serious injection site reaction | HLT = 'Injection site reaction' and either with serious status, or with severe status and (AE end date/time - AE start date/time) \geq 24 hours or ongoing |
| Severe or serious infection | Primary SOC = 'Infections and infestations' and with severe or serious status |
| Parasitic infection | The Infection Type 'Parasitic' was checked on the eCRF page "Infection Event Form" |
| Opportunistic infection | The question "Has the AE been assessed as opportunistic infection?" is answered "Yes" on the eCRF page "Infection Event Form" |
| Drug-related hepatic disorder | Drug-related hepatic disorders - Comprehensive search narrow SMQ (20000006) |
| Pregnancy | "Pregnancy" checked on the Pregnancy eCRF page as reported by the investigator |
| Symptomatic overdose with IMP | The answers for both "Symptomatic Overdose" and "Overdose of SAR231893" are "Yes" on the eCRF page "Adverse Event". |
| Symptomatic overdose with noninvestigational medicinal product (NIMP) | The answers for both "Symptomatic Overdose" and "Overdose of NIMP" are both "Yes" on the eCRF page "Adverse Event". |
| Other selected AE grouping | |
| Injection site reaction | HLT = 'Injection site reaction' |
| Malignancy | Sub-SMQ (20000091) – Malignant or unspecified tumors |
| Partner pregnancy | "Partner Pregnancy" checked on the Pregnancy eCRF page as reported by the investigator |
| Conjunctivitis (narrow) | PT in (Conjunctivitis, Conjunctivitis allergic, Conjunctivitis bacterial, Conjunctivitis viral, Atopic keratoconjunctivitis) |
| Conjunctivitis (broad) | PT in (Conjunctivitis, Conjunctivitis allergic, Conjunctivitis bacterial, Conjunctivitis viral, Atopic keratoconjunctivitis, Blepharitis, Dry eye, Eye irritation, Eye pruritus, Lacrimation increased, Eye discharge, Foreign body sensation in eyes, Photophobia, Xerophthalmia, Ocular hyperaemia, Conjunctival hyperaemia) |
| Eosinophilia | HLT = 'Eosinophilic disorders' or PT = 'Eosinophil count increased' |
| Keratitis | PT in (Keratitis, Allergic keratitis, Ulcerative keratitis, Atopic keratoconjunctivitis, Herpes ophthalmic, Ophthalmic herpes simplex, Corneal infection) |

The following summary will be provided:

- All treatment-emergent AESIs and other selected AE groupings identifiable by MedDRA terms, by AESI category and PT, showing the number (%) of participants will be presented by decreasing incidence of PT within each AESI category.

3.5.3 Additional safety assessments

3.5.3.1 Laboratory variables, vital signs and electrocardiograms (ECGs)

The following laboratory variables, vital signs and electrocardiogram (ECG) variables will be analyzed. They will be converted into standard international units.

- Hematology:
 - Red blood cells and platelets and coagulation: erythrocytes, hemoglobin, hematocrit, platelet count
 - White blood cells: leukocytes, with five-part differential count (neutrophils, lymphocytes, monocytes, basophils, eosinophils)
- Clinical chemistry:
 - Metabolism: glucose, total cholesterol, total protein, creatine phosphokinase (CPK), albumin
 - Electrolytes: sodium, potassium, chloride, bicarbonate
 - Renal function: creatinine, blood urea nitrogen
 - Liver function: alanine aminotransferase (ALT), aspartate aminotransferase (AST), alkaline phosphatase (ALP), total bilirubin
- Vital signs: systolic and diastolic blood pressure, heart rate, respiratory rate, body temperature, body weight, height.
- ECG variables: heart rate, PR, QRS, QRS axis, QT, QTc, RR.

Data below the lower limit of quantitation/detection limit (LLOQ) will be replaced by half of the LLOQ, data above the upper limit of quantification will be replaced by ULOQ value.

Quantitative analyses

When relevant, for laboratory variables, vital signs and ECG variables above, descriptive statistics for results and changes from baseline will be provided for each analysis window, the last value and the worst value (minimum and/or maximum value depending on the parameter) during the on-treatment period. These analyses will be performed using central measurements only for laboratory variables.

For each continuous parameter for laboratory variables and vital signs, mean change from baseline with corresponding standard error will be plotted over time.

Analyses according to PCSA

Potentially clinically significant abnormality (PCSA) analyses will be performed based on the PCSA list currently in effect at Sanofi at the time of the database lock. For parameters for which no PCSA criteria are defined, similar analyses will be done using the normal range, if applicable.

Analyses according to PCSA will be performed based on the worst value during the treatment-emergent period, using all measurements (either local or central, either scheduled, nonscheduled or repeated).

For laboratory variables, vital signs and ECG variables above, the incidence of participants with at least one PCSA during the treatment-emergent period will be summarized regardless of the baseline level and/or according to the following baseline status categories:

- Normal/missing
- Abnormal according to PCSA criterion or criteria.

For laboratory variables, a listing of participants with at least 1 PCSA during the treatment-emergent period will be provided and will display the whole profile over time of all parameters of the corresponding biological function. In this listing, baseline, endpoint value and individual values will be flagged when lower or higher than the lower or upper laboratory limits and/or when reaching the absolute limit of abnormality criteria.

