17.7.2.5.2 Duration of study participation

17.7.2.5.2.1 Duration of study participation for each patient

The total duration, per patient, is of approximately 68 weeks.

For each patient, this includes the following 3 periods:

- **Screening period:** 4 ±1 weeks.
- **Treatment period:** 52 weeks open-label treatment (1 year) with last dosing at Week 50 for q2w and at Week 48 for q4w.
- **Post-treatment period:** 12 weeks.

17.7.2.5.2.2 Determination of end of clinical trial (all patients)

See [Section 6.2.2](#).

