Laboratory tests, vital signs, physical examination, or electrocardiogram (ECG) abnormalities are to be recorded as AEs only if they meet the criteria defined in [Section 10.4.3](#), and are assessed as described in [Section 17.7.2.8.3.5](#), [Section 17.7.2.8.3.2](#), [Section 9.1.2](#) and [Section 17.7.2.8.3.4](#). In addition to assessment of primary endpoint, below parameters are used on an ongoing basis during the study to monitor safety of participants and will be presented in a descriptive manner.

17.7.2.8.3.2 Vital signs

Vital signs including blood pressure (mmHg), heart rate (beats per minute), respiratory rate (breaths per minute), and body temperature (degrees Celsius) will be measured at each onsite visit except for IMP administration only visits.

Vital signs will include height (cm) and body weight (kg). Height will be measured at each onsite visit except for the IMP administration only visit and Visit 9 (Week 36). Weight will be measured at each onsite visit except for the IMP administration only visit.

17.7.2.8.3.3 Physical examinations

See [Section 9.1.2](#).

17.7.2.8.3.4 Electrocardiograms

Electrocardiogram (ECG) variables will be recorded by a standard 12-lead ECG. ECGs will be performed at screening, EOT, and EOS (see [Section 17.7.2.2.2](#)).

17.7.2.8.3.5 Clinical laboratory values

Abnormal laboratory values that are considered to be clinically significant by the Investigator should be repeated as soon as possible after receiving the laboratory report to rule out laboratory error. Persistent abnormal laboratory values should be repeated until they return to normal or until an etiology of the persistent abnormality is determined.

Globally, guidelines for blood collection volume limits for pediatric studies range between 1% and 5% of total blood volume (TBV) for a single draw (or during a 24-hour period) and up to 10% of TBV over 8 weeks [\(9\)](#). Scheduled collections in the current protocol, for the smallest possible patient (15 kg), remain within this limit for every 3 months. For all scheduled blood collection visits, the total volume does not exceed 1.5 mL/kg for the smallest possible patient.

Refer to [Section 17.7.2.2.2](#) for the description of the clinical laboratory evaluations and the schedule of laboratory evaluations performed throughout this study. The clinical laboratory parameters that will be measured in safety are:

Hematology:

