- For quantitative safety parameters, descriptive statistics will be used to summarize results and change from baseline values for each analysis set of safety population by the treatment category. Summaries will include the endpoint value and/or the worst on-treatment value. The endpoint value is commonly defined as the value collected at the date of last IMP dose +1 dose interval (14 days for last IMP as 100/200 mg q2w and 28 days for last IMP as 300 mg q4w) or the end of treatment visit. If this value is missing, this endpoint value will be the closest value prior to the last administration of IMP + 1 dose interval. The worst value is defined as the nadir and/or the peak post-baseline (up to last administration of IMP + 1 dose interval) according to the direction (minimum or maximum) of the abnormality as defined in the PCSA list.
- All of the values including unscheduled measurements will be assigned to the appropriate safety analysis visit window. The safety analysis visit window is defined in [Section 2.5.3](#).
- The analysis of the safety variables will be essentially descriptive and no systematic testing is planned.

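### Japan SAP 3.5.3.1: the on-treatment cut-off makes no allowance for the ±3-day EOT window, so a compliant EOT visit can be left out of the last-value and worst-value safety rows

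*SAP*

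**What the plan says.** Section 3.5.3.1 of the Japan SAP plans three kinds of descriptive summary for laboratory, vital-sign and ECG variables: one per analysis window, and one each for "the last value and the worst value (minimum and/or maximum value depending on the parameter) during the on-treatment period". Section 3.1 opens that period at the first dose and closes it, on the two q2w regimens, as follows: "last administration of the IMP + 14 days for participants with IMP on 100 mg/200 mg q2w regimen". On the q4w regimen the allowance is 28 days instead of 14. The date of the EOT visit plays no part in the definition.

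Protocol Section 17.7.2.5.2.1 sets treatment "with last dosing at Week 50 for q2w and at Week 48 for q4w". Section 17.7.2.9 allows treatment-period visits, including EOT at Week 52, within 3 days either side of target. The Week 48 telephone contact (17.7.2.9.1.4.10, which points to 10.1.2.10) asks families to keep 14 ± 3 days (q2w) or 28 ± 3 days (q4w) between the last dose and EOT. On ECGs, Section 17.7.2.8.3.4 says "ECGs will be performed at screening, EOT, and EOS".

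The main-study SAP (Section 2.4.5) is more tolerant for its endpoint value. After naming the point one dose interval past the last dose, it adds an alternative: "28 days for last IMP as 300 mg q4w) or the end of treatment visit".

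**The concern.** The cut-off for the last and worst values has no tolerance, whereas the visit that should supply the final on-treatment measurement has 3 days of it. Data collected as the protocol asks can therefore fall outside the period because of scheduling alone.

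Two consequences follow. The last-value row can mix Week 52 results with much older ones, depending on which day the family came in. For the ECG, EOT is the only scheduled recording between the first dose and the end of the on-treatment period, so a child with a slightly late EOT has nothing scheduled to put in either row. The number of children in the last-value ECG row could then differ from the number in the Week 52 row, with no clinical reason. With 13 children across three regimens, one or two such gaps would be visible in the tables.

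**Working it through.** **Inputs**
- On-treatment end: last dose + 14 days (q2w) or + 28 days (q4w) (Japan SAP 3.1).
- Planned last dose: Week 50 (q2w), Week 48 (q4w) (Protocol 17.7.2.5.2.1).
- EOT target: Day 365 (Japan SAP 5.4, Table 6), window ± 3 days (Protocol 17.7.2.9).
- Permitted gap from last dose to EOT: 14 ± 3 or 28 ± 3 days (Protocol 10.1.2.10).
- Enrolled: 13 (Japan SAP 1.1).

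**Step 1: reproduce the SAP's day numbering.** Day = 7 × week + 1. Week 52 gives 7 × 52 + 1 = 365, as in Table 6. Week 36 gives 253, also as in Table 6.

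**Step 2: end of the on-treatment period with doses on schedule.**
- q2w: (7 × 50 + 1) + 14 = 351 + 14 = Day 365.
- q4w: (7 × 48 + 1) + 28 = 337 + 28 = Day 365.

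The exposure formula in Japan SAP 3.5.1 agrees: 351 − 1 + 15 = 365 days and 337 − 1 + 29 = 365 days. The period therefore ends on the EOT target day itself under both regimens.

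**Step 3: permitted EOT days against that end.** EOT may fall on Days 362-368. Days 362-365 are inside the period; Days 366, 367 and 368 are outside. That is 3 of 7 days, or 43%. Applied to 13 children, 13 × 3/7 = 5.6.

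**Step 4: let the last dose move as well.** What matters is the gap, not the calendar day. A gap of 15-17 days (q2w) or 29-31 days (q4w) is permitted by the protocol and excluded by the SAP. A last dose on Day 354 with EOT on Day 368 (q2w, gap 14) stays inside. A last dose on Day 350 with EOT on Day 365 (gap 15) falls outside although EOT is on target. Shift the last dose and EOT each by −3 to +3 days, and keep only pairs whose gap is within 3 days of the interval. The pairs with differences 0, ±1, ±2, ±3 number 7 + 12 + 10 + 8 = 37, and those with a gap that is too long number 6 + 5 + 4 = 15. So 15 of 37 permitted combinations put EOT outside. This counts combinations; it is not a probability.

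**Step 5: what fills the row instead.**
- Haematology, chemistry, weight and the other vital signs: Week 36, which is 365 − 253 = 112 days before the EOT target.
- Height: not measured at Week 36 (Protocol 17.7.2.8.3.2), so Week 24, Day 169.
- ECG: no scheduled value.

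**Step 6: where the late EOT result still appears.**
- By-window summary: Table 6 assigns laboratory and vital-sign results on Days 309-406 to Week 52. For the ECG the window runs from after the first dose to Day 406. Day 368 is well inside.
- Potentially clinically significant abnormalities: Section 3.5.3.1 uses the treatment-emergent period, last dose + 98 or + 112 days. On schedule that is 351 + 98 = 449 and 337 + 112 = 449.

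**The case against.** The strongest reply is that little is lost. A reader might infer that a late EOT result disappears and that a child's only on-treatment ECG goes unreported. The documents do not support that: as Step 6 shows, the result is summarised at Week 52 with its change from baseline, and any abnormality still counts. Without unscheduled ECGs, the last and worst ECG rows merely repeat the Week 52 row, so what goes missing is a second entry for the same recording. Unscheduled measurements may also fill a gap, and all these tables are descriptive. This stands, and it limits the point to two rows.

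A reader might also infer that the main-study SAP avoids the problem altogether. It does so for the endpoint value and, through the maximum rule in Section 2.5.3, for its visit windows. Its worst value stops at last dose + one interval, as in Japan. The main SAP is therefore a precedent for the last value only.

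Thirdly, extending the period to any EOT date would overshoot. Where the decision to stop comes late, Protocol 17.7.2.9 sets the early EOT as soon as possible, with no upper limit from the last dose, so off-drug values could be labelled on-treatment. That objection is right and is the reason for the cap in the fix.

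Finally, the on-treatment qualifier in 3.5.3.1 could be read as attaching to the worst value alone. That is the less natural reading. It would leave the last value with no cut-off, so that it could come from the post-treatment visit, and the text would still need clarifying.

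**Conclusion.** The point holds for the last-value and worst-value rows and no further. A protocol-compliant EOT visit held 15-17 days (q2w) or 29-31 days (q4w) after the last dose is excluded from both rows. The figure of 3 in 7 permitted days, about 5-6 of 13 children, is an illustration. It requires all 13 to reach EOT, last doses exactly on schedule and EOT days spread evenly. The Week 48 reminder ties the last dose to the EOT date, so the two may move together, and the documents give no basis for an expected count. No safety signal is hidden. The cost of leaving the text as it is lies in inconsistent row counts and some last values about 16 weeks old (112 days). This is a cheap improvement, not a threat to the substudy's conclusions.

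**What to change.** In Japan SAP 3.5.3.1, state that the last value is the EOT-visit value when that visit (or an early EOT) falls no later than last dose + one dose interval + 3 days, that is + 17 days for q2w or + 31 days for q4w. Otherwise it is the latest value in the on-treatment period. This follows the main SAP's endpoint rule, with a cap added. Apply the same 3-day tolerance to the worst value, and record that this goes slightly beyond the main SAP. Do not extend the period without limit to a late early-EOT visit.

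With doses on schedule the limit becomes Day 368 under both regimens, so every EOT on Days 362-368 counts. The cost is a sentence or two of SAP text and a small programming change, with no new data. The one drawback is a minor difference from the main study's worst-value definition.
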